#### **13.3.4 Subject Recruitment**

Advertisements approved by IRBs/ECs and investigator databases may be used as recruitment procedures. Use of ethics committee approved, generic, prescreening questionnaire to assess basic subject characteristics to determine general eligibility for this study is allowed.

GSK CH will have an opportunity to review and approve the content of any study recruitment materials directed to potential study subjects before such materials are used.

#### **13.3.5 Reporting of Safety Issues and Serious Breaches of the Protocol or ICH GCP**

Within GSK CH a serious breach is defined as a breach likely to affect to a significant degree the safety and rights of a subject or the reliability and robustness of the data generated in GSK CH sponsored human subject research studies.

In the event of any prohibition or restriction imposed (i.e., clinical hold) by an applicable competent authority in any area of the world, or if **CCI** [REDACTED] is aware of any new information that might influence the evaluation of the benefits and risks of the investigational product, GSK CH should be informed immediately.

In addition, **CCI** [REDACTED] will inform GSK CH immediately of any urgent safety measures taken by the investigator/designee to protect the study subjects against any immediate hazard, and of any serious breaches of this protocol or of ICH GCP that the investigator/designee becomes aware of.

#### **13.4 Posting of Information on Publicly Available Clinical Trial Registers**

Study information from this protocol will be posted on publicly available clinical trial registers before enrollment of subjects begins in accordance with applicable GSK CH processes.

GSK CH intends to make anonymized subject-level data from this trial available to external researchers for scientific analyses or to conduct further research that can help advance medical science or improve patient care. This helps ensure the data provided by trial subjects are used to maximum effect in the creation of knowledge and understanding

### **13.5 Provision of Study Results to Investigators**

Where required by applicable regulatory requirements, a local PI signatory will be identified for the approval of the clinical study report. The local PI will be provided reasonable access to statistical tables, figures, and relevant reports and will have the opportunity to review the complete study results at a GSK CH site or other mutually agreeable location.

GSK CH will also provide the local PI with the full summary of the study results. The local PI is encouraged to share the summary results with the study subjects, as appropriate.

The procedures and timing for public disclosure of the results summary and for development of a manuscript for publication will be in accordance with GSK CH Policy.

A manuscript will be progressed for publication in the scientific literature if the results provide important scientific or medical knowledge.

### **13.6 Records Retention**

Following closure of the study, **CCI** must maintain all study records (except for those required by local regulations to be maintained elsewhere), in a safe and secure location.

The records (study/ site master file) must be maintained to allow easy and timely retrieval, when needed (e.g., for a GSK CH audit or regulatory inspection) and must be available for review in conjunction with assessment of the facility, supporting systems, and relevant site staff.

Where permitted by local laws/regulations or institutional policy, some or all of these records can be maintained in a format other than hard copy (e.g., microfiche, scanned, electronic); however, caution needs to be exercised before such action is taken.

**CCI** must ensure that all reproductions are legible and are a true and accurate copy of the original and meet accessibility and retrieval standards, including re-generating a hard copy, if required. Furthermore, the investigator must ensure there is an acceptable back-up of these reproductions and that an acceptable quality control process exists for making these reproductions.

**CCI** must assure that the subject's anonymity will be maintained. On eCRFs or other documents submitted to GSK CH, subjects should not be identified by their names or initials, but by an identification code. **CCI** should keep a separate log of subjects' codes, names, and addresses. Documents not for submission to GSK CH, e.g.,

subjects' written consent forms, should be maintained by the investigator in strict confidence.

Records and documents, including signed eIC, pertaining to the conduct of this study must be retained by the investigator as per the signed contractual agreement, from the issue of the final Clinical Study Report (CSR) or equivalent summary, unless local regulations or institutional policies require a longer retention period. The minimum retention time will meet the strictest standard applicable to that site for the study, as dictated by any institutional requirements or local laws or regulations, GSK CH standards/procedures, and/or institutional requirements.

No study document should be destroyed without a prior written agreement between GSK CH and the investigator. The investigator must notify GSK CH of any changes in the archival arrangements, including, but not limited to, archival at an off-site facility or transfer of ownership of the records in the event the investigator is no longer associated with the site.

### **13.7 Conditions for Terminating the Study**

Premature termination of this study may occur because of a regulatory authority decision, change in opinion of the IRB/EC, or study product safety problems, or at the discretion of GSK CH.

If a study is prematurely terminated, GSK CH will promptly notify **CCI** [REDACTED]. After notification, **CCI** [REDACTED] must promptly contact all participating subjects and should assure appropriate therapy/ follow-up for the subjects. As directed by GSK CH, all study materials must be collected and all eCRF's completed to the greatest extent possible. Where required by the applicable regulatory requirements, GSK CH should inform the regulatory authority(ies) and the investigator should promptly inform the IRB/EC and provide the IRB/EC a detailed written explanation of the termination or suspension.

If the IRB/EC terminates or suspends its approval/favorable opinion of a trial, the local PI or designee should promptly notify the GSK CH and provide GSK CH with a detailed written explanation of the termination or suspension.

Upon completion or premature discontinuation of the study, the GSK CH monitor will conduct site closure activities with **CCI** [REDACTED] as appropriate, in accordance with applicable regulations including GCP, and GSK CH Standard Operating Procedures.

## 15 APPENDICES

### 15.1 ABBREVIATIONS

The following is a list of abbreviations that may be used in the protocol.

**Table 15-1 Abbreviations**

Abbreviation	Term
AE	Adverse event
ANOVA	Analysis of variance
COACH	Clinical Oversight and Coordination Hub
CRF	Case report form
EC	Ethics committee
eCRF	Electronic Case Report Form
EudraCT	European Clinical Trials Database
FDA	Food and Drug Administration (United States)
GCP	Good Clinical Practice
HSI	Human Subject Information
IB	Investigator's brochure
ICH	International Conference on Harmonisation
ID	Identification
IEC	Independent Ethics Committee
IRB	Institutional review board
IRC	Internal review committee
MedDRA	Medical Dictionary for Regulatory Activities
N/A	Not applicable
OTC	Over the counter (reference to medications available without prescription)
PI	Principal investigator
QC	Quality control
QoL	Quality of Life
RCT	Randomized Clinical Trial
RWD	Real World Data
RWE	Real World Evidence
SAE	Serious adverse event
SOP	Standard operating procedure

## 15.2 STUDY QUESTIONNAIRES

### 15.2.1 Wisconsin Upper Respiratory Symptom Survey – 21 (WURSS-21)

**Wisconsin Upper Respiratory Symptom Survey – 21 --- Daily Symptom Report**

Day:	Date:	Time:	ID:
------	-------	-------	-----

Please fill in one circle for each of the following items:

	Not sick 0	Very mildly 1	Mildly 2	Moderately 3	Severely 4	5	6	7
How sick do you feel today?								

Please rate the average severity of your cold symptoms over the last 24 hours for each symptom:

	Do not have this symptom 0	Very mild 1	Mild 2	Moderate 3	Severe 4	5	6	7
Runny nose								
Plugged nose								
Sneezing								
Sore throat								
Scratchy throat								
Cough								
Hoarseness								
Head congestion								
Chest congestion								
Feeling tired								

Over the last 24 hours, how much has your cold interfered with your ability to:

	Not at all 0	Very mildly 1	Mildly 2	Moderately 3	Severely 4	5	6	7
Think clearly								
Sleep well								
Breathe easily								
Walk, climb stairs, exercise								
Accomplish daily activities								
Work outside the home								
Work inside the home								
Interact with others								
Live your personal life								

Compared to yesterday, I feel that my cold is...

Very much better 0	Somewhat better 1	A little better 2	The same 3	A little worse 4	Somewhat worse 5	Very much worse 6
						

WURSS-21® (Wisconsin Upper Respiratory Symptom Survey) 2004

Created by Bruce Barrett MD PhD et al., UW Department of Family Medicine, [name]

Property of GSK Consumer Healthcare - Confidential

May not be used, divulged, published or otherwise disclosed without the consent of GSKCH

CCI

Clinical Protocol Template v9.0

### 15.2.2 Additional QoL Questions

#### Baseline Questions (pre-treatment):

Instructions: Considering the last 24 hours, please read each question and choose the answer that best reflects your experience with your nasal congestion before the use of Otrivine.

- Before using Otrivine, is your nasal congestion/cold making you snore during the night? (\*For those with sleeping partners only)
- Before using Otrivine, is your nasal congestion/cold making you slow in your responses?
- Before using Otrivine, is your nasal congestion/cold making you self-conscious about how you sound?
- Before using Otrivine, is your nasal congestion/cold affecting your sense of smell?
- Before using Otrivine, is your nasal congestion/cold affecting your sense of taste?
- Before using Otrivine, is your nasal congestion/cold making you self-conscious around people?
- Before using Otrivine, is your nasal congestion/cold making you less energetic than usual?
- Before using Otrivine, is your nasal congestion/cold making you less motivated than usual?

#### Post treatment Questions (asked every day in the morning)

Instructions: Considering the past 24 hours, please read each question and choose the answer that best reflects your experience with Otrivine use and your nasal congestion.

- After using Otrivine, is your nasal congestion/cold making you snore during the night? (\*For those with sleeping partners only)
- After using Otrivine, is your nasal congestion/cold making you slow in your responses?
- After using Otrivine, is your nasal congestion/cold making you self-conscious about how you sound?
- After using Otrivine, is your nasal congestion/cold affecting your sense of smell?
- After using Otrivine, is your nasal congestion/cold affecting your sense of taste?
- After using Otrivine, is your nasal congestion/cold making you self-conscious around people?
- After using Otrivine, is your nasal congestion/cold making you less energetic than usual?
- After using Otrivine, is your nasal congestion/cold making you less motivated than usual?

Property of GSK Consumer Healthcare - Confidential

[figure not shown]
May not be used, divulged, published or otherwise disclosed without the consent of GSKCH

CCI

Clinical Protocol Template v9.0

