### 2.2 Background

Otrivine (xylometazoline hydrochloride) is a nasal decongestant spray that constricts nasal blood vessels and increases nasal airflow, enabling individuals with a blocked nose to breathe more easily. This is a well-known and commonly used decongestant; different versions of this product have been marketed in numerous countries and used by consumers for decades.

A double-blind, placebo-controlled, parallel group study by Eccles (Eccles et al., 2008) investigated the efficacy of the Otrivine nasal spray in patients with common cold. Twenty-nine patients were treated with xylometazoline hydrochloride 0.1%, and 32 patients treated with a placebo (saline solution); 1 spray 3 times a day for up to 10 days was the posology used. The primary objective of the study was to determine the

decongestant effect (via nasal conductance); and the secondary objectives were to determine the peak subjective effects (visual analog scale), duration of relief of nasal congestion and total and individual cold symptoms. In addition, any effects on sleep, tiredness, general well-being and smell/taste were studied as exploratory variables with a daily diary. Adverse events (AEs) were also assessed. The decongestant effect of xylometazoline hydrochloride was significantly greater than placebo, as shown by the nasal conductance at 1 hour. Peak subjective effect (VAS assessment) was also significantly positive. Nasal conductance was significantly superior for up to 10 hours. Compared with placebo, xylometazoline hydrochloride significantly improved the total common cold symptom score on day 1 of treatment (xylometazoline hydrochloride 25.71 versus placebo 35.79; ( $p=0.0221$ )) and significantly improved individual common cold symptoms on day 1 (blocked nose, sore throat, and earache), day 2 (blocked nose), day 5 (runny nose), and day 10 (runny nose) of treatment. Xylometazoline hydrochloride-associated significant improvement of total and some individual common cold symptoms scores lead to significantly greater patient general evaluation and satisfaction with treatment.

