## **4.2 Scientific Rationale for Study Design**

RWE studies reflect product use in everyday life. They offer the opportunity to gather information on currently marketed products to not only substantiate clinical evidence, but to provide additional information on the target patient population.

The Wisconsin Upper Respiratory Symptom Survey (WURSS) is an evaluative illness-specific quality of life instrument, designed to assess the negative impact of acute upper respiratory infection, presumed viral (the common cold). WURSS-21 is the short version of this validated survey.

Subjects with nasal congestion due to common cold, who seek to treat with study treatment (Otrivine) will complete WURSS-21 and an additional GSK CH designed QoL

Property of GSK Consumer Healthcare - Confidential

May not be used, divulged, published or otherwise disclosed without the consent of GSKCH

questionnaire once every 24-hours. Study treatment use will be reported via diaries. These measures will provide GSK CH with information on the effects of Otrivine over the natural course of their common cold. This will enable GSKCH to evaluate the daily effects that may be attributable to the study treatment.

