### **12.3.2 Secondary Analysis**

For the secondary objective, subjects' pre-treatment score will be used to determine the effect of Otrivine on additional QoL parameters. Median post-treatment scores will be presented for each day of treatment through Day 7 or until data are no longer provided due to nasal symptom resolution, whichever comes first.

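### The eight additional QoL items are worded differently before and after treatment, and the post-treatment wording cues a product effect

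*Protocol*

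**What the plan says.** Protocol Section 4.2 states that subjects "will complete WURSS-21 and an additional GSK CH designed QoL" questionnaire. That questionnaire is printed in Section 15.2.2 in two forms.

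- **Baseline form.** The instruction asks the subject to "choose the answer that best reflects your experience with your nasal congestion before the use of Otrivine". The energy item reads "Before using Otrivine, is your nasal congestion/cold making you less energetic than usual".
- **Post-treatment form, every morning.** The instruction asks the subject to "choose the answer that best reflects your experience with Otrivine use and your nasal congestion". The same item reads "After using Otrivine, is your nasal congestion/cold making you less energetic than usual".

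Under Treatment Period, Sections 1.1 and 4.1 add that the morning answers to these questions are to take account of what the previous day's product did.

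Section 12.3.2 says that "subjects' pre-treatment score will be used to determine the effect of Otrivine on additional QoL parameters", and then that "Median post-treatment scores will be presented for each day of treatment through Day 7", or until symptom resolution ends the data. It names no test. Sections 1.1 and 3 define the secondary endpoint as the score after use on Days 1 to 7 for each of the eight factors. The study has no randomisation (5.4) and no blinding (6.5).

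**The concern.** A before-and-after comparison needs the same question at both times. Here the stem and the instruction both change at the moment treatment starts, and the morning prompt is added. The post-treatment version ties the answer to the product: the subject is asked about the time after use, about experience with use, and with the product's effects in mind. A subject who chose to treat, and who knows what was taken, can easily hear this as a question about whether the spray worked.

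With one arm, the wording and the treatment period change together for everyone. If the wording moves the answers, that movement becomes part of the pre-to-post difference, and no later analysis can take it out. Section 12.3.2 then reads that difference as the effect of Otrivine. All eight secondary factors are exposed in the same way.

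**Working it through.** The protocol gives no figure for these items, so the main check sets the texts side by side.

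1. **Stems (15.2.2).** The eight baseline items and eight post-treatment items pair one to one. In 8 of 8 pairs the opening changes from *Before* to *After*. The rest of each item is the same: snoring, slow responses, sound of the voice, smell, taste, self-consciousness around people, energy and motivation.
2. **Recall period (15.2.2).** Both instructions set 24 hours, so there is no change.
3. **Object of the answer (15.2.2).** Baseline: congestion before use. Post-treatment: use of the product together with congestion. This changes.
4. **Product name.** Otrivine appears in every stem and in the instruction of both forms. Naming the product is therefore not the difference; the Before/After framing and the shift to experience with use are.
5. **Prompt (1.1, 4.1).** The reminder about the previous day's product attaches to the morning assessments only. It has no baseline counterpart.
6. **Use of the scores (12.3.2).** The baseline answer is the stated reference for a product effect, so the two wordings are set against each other.
7. **Offsets (5.4, 6.5).** There is no concurrent group answering the *After* wording without the product.
8. **Comparison instrument (15.2.1).** WURSS-21 is completed alongside these items, has a single form, and names no product. A neutral daily stem is therefore workable in this study.
9. **The protocol's own standard elsewhere.** Section 10.4 requires open-ended, non-leading questioning for adverse events and care not to introduce bias. The secondary items do not meet that standard.

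**Scale, as an assumption only.** The documents give no size for a wording effect. Suppose wording alone shifts the mean answer by *b* standard deviations of the change and nothing else changes. For a two-sided 5% paired t-test on the 100 completers of Section 12.1, the noncentrality is b × √100:

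- b = 0.10: noncentrality 1.0, significant in about 17% of trials
- b = 0.20: noncentrality 2.0, about 51%
- b = 0.27: noncentrality 2.7, about 76%

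The last value equals the standardised effect used for the sample size in 12.1. Section 12.3.2 plans no such test, so these figures show only that a modest shift could pass for an improvement. They do not estimate the shift.

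**The case against.** The case for leaving the items alone has real substance.

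- **The forms are closely parallel.** Content and recall match, and both name the product. This stands. A reader might infer that the two forms measure different things; the texts support only that the wording is not equivalent.
- **The endpoint is a post-use score, shown as daily medians with no test.** This also stands and limits the harm. The comparison enters only through the opening sentence of 12.3.2, but that sentence states a purpose of determining a product effect.
- **Attribution is weak anyway.** Section 4.2 concedes confounding by natural resolution, and open-label expectation also bears on WURSS-21. That is true. The wording change is still a separate source of error, and unlike the others it can be removed by editing text.

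Four stronger readings are tempting but not supported:

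- **A shortened recall window.** Section 2.2 reports that "Nasal conductance was significantly superior for up to 10 hours", which might suggest that post-treatment answers cover only the hours after a spray. That result concerns airflow in an earlier trial, both forms fix 24 hours, and three permitted uses a day could span more than 24 hours (3 × 10 = 30).
- **Asking about use that never happened.** Section 8.2.1 ends the daily forms one day after the last dose, so the final form follows a day of use. Only a skipped day in mid-course remains.
- **56 affected answers per subject.** 8 items × 7 days = 56 is a maximum. The snoring item is only for those with a sleeping partner (7 × 7 = 49), and 8.2.1 speaks of six post-treatment days (8 × 6 = 48, or 7 × 6 = 42).
- **Contamination of WURSS-21.** The morning prompt stands directly after the additional questions, and the WURSS-21 form carries its own product-free instruction.

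**Conclusion.** The point holds in a limited form. All eight additional QoL items change wording between baseline and follow-up, and the follow-up wording, its instruction and the morning prompt together cue a product effect. In an open-label study with no control arm, a wording effect cannot be separated from real change, so these items cannot carry the attribution to Otrivine that 12.3.2 gives them.

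The size of the effect is unknown and cannot be derived from the documents. That it favours the product is the most plausible direction, but this is a judgement and the documents do not show it. The conclusion assumes that the app displays the items as printed in 15.2.2. It reaches only the secondary items; the primary WURSS-21 endpoint and the sample size are unaffected.

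**What to change.** 1. In 15.2.2, use one identical, product-neutral stem and one instruction at baseline and on every post-treatment day. For example: *Over the past 24 hours, has your nasal congestion/cold made you less energetic than usual?*
2. In 1.1 and 4.1, delete the prompt that tells subjects to consider the product's effects when answering.
3. Take product use from the eDiary, which already records the number and time of sprays (9.3).
4. If the forms are already in use, state in 12.3.2 that pre/post differences on these items are descriptive and are not attributable to Otrivine, because the wording differs.

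**Cost.** The items are the sponsor's own, so the sponsor can edit them. The change still needs a protocol amendment with prior IRB/EC approval (13.3.1) and an update to the study app. Scores collected under the old wording could not be pooled with those collected under the new, so a change part-way through would split the secondary data.

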**Please rate each of the statements:**

**End of the study questions**

**• How would you rate your satisfaction with the treatment?**

Very Satisfied

Satisfied

Neutral

Dissatisfied

Very Dissatisfied

Please explain why you chose Very Satisfied/Satisfied/Neutral/Dissatisfied/Very Dissatisfied?

